Exclusion Criteria	
 1) Pre-existing diagnosis of diabetes mellitus, fasting blood glucose >115 mg/dl, or hemoglobin A1c level >6.0% because these are all evidence of inadequate beta-cell mass. 2) Use of any of the following treatments in the 30 days prior to enrollment: insulin, metformin, sulfonylureas, glinides, thiazolidinediones, GLP-1 agonists, DPP-4 inhibitors, or amylin. 3) IgA deficiency (serum level <5 mg/dL), which has been associated with hypersensitivity to alpha-1 antitrypsin. 4) ALT or AST >2.5 times the upper limit of normal (ULN). Bilirubin >ULN, unless due to benign diagnosis such as Gilbert's. 5) Known history of HIV infection, hepatitis B (chronic), or hepatitis C (chronic). 6) History of tuberculosis (latent or active disease), or positive TB skin test. 7) History of symptomatic fungal lung infection. 8) History of multiple sclerosis, transverse myelitis, Guillain Barre, or other suspected demyelinating disease, due to risk of exacerbation of these conditions with use of etanercept; or prior history of systemic lupus erythematosus 9) Any of the following hematologic abnormalities: severe anemia (hgb <10 g/dL), thrombocytopenia (<150/mm3), or neutropenia (<1.0 x10⁹/L). 10) Current use or expected use of oral or injected corticosteroids, or any mediation likely to affect glucose tolerance. However, use of hydrocortisone for physiologic replacement, or use of any topical, inhaled, or intranasal glucocorticoid is permitted. 11) Current or expected use of any other immunosuppressive agent. 12) Known hypersensitivity to etanercept or A1AT. 13) Any condition that is likely, in the opinion of the patient's medical providers, to necessitate use of TNF alpha therapeutically in the future (such as psoriatic arthritis). 14) Known coagulopathy, or need for anticoagulant therapy preoperatively (coumadin, enoxaparin), or any history of pulmonary embolism. 15) For females, plans to become pregnant or unwillingness to use birth control for the study duration. 16) Inability to comply with the study protocol. 17) Untreated psychiatric illness that may interfere with ability to give informed consent, or other developmental delay or neurocognitive disorder that impairs with a patient's ability to consent on their own behalf. 18) Any other medical condition that, in the opinion of the investigator, may interfere with the patient's ability to successfully and safely complete the trial.

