Treatment Description	Forty-five patients undergoing TP-IAT (day 0) at a single center will be randomized 1:1:1 to receive during the peri-operative period either: 1) etanercept (50 mg on day 0 SQ; 25 mg SQ on days 3, 7, 10, 14, and 21), 2) alpha-1 antitrypsin (90 mg/kg IV infusion on days -1, and +3, 7, 14, 21, and 28 post-transplant) or 3) standard care .
Study Procedures	
Patients will be seen within 4 weeks prior to surgery (screening/baseline), and at day 90 (\pm 14 days), day 365 (\pm 28 days), and day 730 (\pm 56 days) post-transplant. These will occur over two days. The following metabolic testing will be performed at each visit:
 
 1) 10 minute IV glucose tolerance test 2) Glucose potentiated arginine induced insulin secretion (GPAIS), performed on same morning as the IVGTT 3) Mixed meal tolerance test (2 hour, Boost HP) 
In addition, patients will have serum draws for mechanistic assessments and safety labs in the first month post-transplant as detailed in the protocol. The mechanistic assessments will include unmethylated insulin DNA and cytokine/chemokine profiles. For long-term follow up of participants, patients will receive routine care subsequent to the day 730 visit, which includes a HbA1c and mixed meal test at yearly intervals. Study investigators will review results from these annual labs and have a telephone follow up with the participant at years 3, 4 and 5 for insulin requirements, blood glucose review, and hypoglycemia history.

Study Abstract

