The first hurdle to a successful islet transplant is the number of islets available, and thus the transplanted islet mass is an important predictor of subsequent diabetes risk (7-9, 21). However significant variability in diabetes outcomes is seen for any given transplanted islet mass. Approximately 70% of IAT recipients with >5000 islet equivalents (IEQ)/kilogram body weight transplanted will achieve insulin independence, while 30% never come off insulin despite the large number of islets infused. In contrast, nearly 10% of those patients with a very low islet mass (<2500 IEQ/kg) will maintain insulin independence, sometimes for years (7). This variability can largely be explained by the difference between the *transplanted* islet mass and the *engrafted* islet mass. Beta cell apoptosis and loss occurs in the immediate post-operative period due to the stress of the procedure and transplant environment. High levels of beta cell apoptosis are observed, particularly in the 7 days after surgery, with apoptosis observed even at 30 days (11, 12). It has been estimated that more than half of the islet mass may be lost in this early post-transplant period in islet transplant recipients (13). The innate inflammatory response, triggered by islet infusion, hypoxia, and hyperglycemic stress, is an important contributor to beta cell loss. In allograft transplant, successful engraftment of transplanted islets, as demonstrated by functional testing at 3 months, is strongly predictive of diabetes remission at 1 year, even more so than the initial number of islets transplanted (22). Thus, this is a critical early window in which to intervene to optimize engrafted islet mass.

Islets are damaged by inflammatory cytokines, which are expressed in the islet graft and upregulated in the TPIAT recipient immediately after surgery

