A local follow up with telephone or face-to-face encounter to review insulin requirements, blood glucose logs, and obtain local mixed meal tolerance test results (part of standard clinical care) will occur at years 3, 4, and 5 (all \pm 2 months) for exploratory data on long-term efficacy. This information will be readily available, as it is part of the standard routine care of all TPIAT recipients at UM.

Subject screening visit

Subjects’ medical history will be reviewed from the electronic medical record and from history obtained from the patient to confirm eligibility. In addition, the following screening assessments will be performed at a screening visit within 4 weeks prior to the scheduled surgery date, after informed consent has been obtained:

- Complete metabolic battery (includes hepatic panel, creatinine, fasting glucose)
- CBC with differential and platelets
- Urine pregnancy test in women with child-bearing potential (if \geq 7 days since screen, repeat prior to first dose of study drug administration; UPT not necessary in females s/p hysterectomy procedure)
- Hepatitis C and hepatitis B serology, HIV ELISA
- IgA level
- Mantoux skin test or Quantiferon (serum) for TB screening
- Hemoglobin A1c level
- Mixed Meal Tolerance Test
- IV glucose tolerance test
- Glucose potentiated arginine-induced insulin secretion

Table. Study Flowchart (year 0-2)

	screening	Days 0-7	Days 7, 14, 21, 28	Day 60	Day 90	Day 365 (Year 1)	Day 730 (Year 2)
Study Visit Assessments (abbreviated)							
Insulin Use/Dose (u/kg/day, endpoint)			X		X	X	X
Mixed Meal Tolerance Test (AUC C-)	X				X	X	X
IVGTT (AIRglu, ACRglu)	X				X	X	X
GPAIS (AIRmax, ACRmax)	X				X	X	X
HbA1c level	X				X	X	X
iPro2 (6 day CGM)					X	X	X
Complete metabolic panel, CBC	X		X*		X	X	X
Random morning C-peptide and glucose			Day 7, 14				
Fasting glucose, C-peptide, creatinine	X		Day 28		X	X	X
Drug safety assessments (PE, hx, labs)		X	X				
Inflammatory cytokines (see text)**		X					
Unmethylated insulin DNA levels**		X	X				
Safety assessment (phone visit for symptoms)				X			
Islet Assessments (see text)		Day 0					

* **Years 3, 4, and 5:** Telephone or face-to-face review of insulin use/dose; labs (HbA1c, clinical MMTT)

** Drawn at multiple time points, as detailed in the methods for Specific Aim #3.

Design and Methods to Evaluate Specific Aim #1

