This is a pilot, parallel-arm study to compare etanercept, A1AT, and control groups; the primary outcome is maximal potentiated arginine induced insulin secretion (AIRmax) measured at 90 days posttransplant. We propose to enroll 15 patients in each group which will give 80% power to detect a difference between any two groups of at least 1.06*(within-group standard deviation of the outcome). From preliminary data for AIRmax measured more than one year post-transplant, the study will have 80% power to detect a difference of at least 33 mU/mL in pairwise comparisons of AIRmax between each of the 3 groups, corresponding to a 24% increase over standard treatment (control group).

The table below shows estimated minimum detectable differences for main outcomes, based on means and standard deviations from preliminary testing performed at 1 year post-transplant (for IVGTT and MMTT) or beyond 1 year post transplant (GPIAS) in this population of TPIAT recipients.

Test	Derived Measure	minimum detectable difference	n	Mean	SD
GPAIS	AIRmax (mU/mL)	33	10	137	31
IVGTT	AIRglu (mU/mL*min)	162	33	169	153
	ACRglu (ng/mL *min)	8.8	36	9.8	8.3
MMTT	AUC C-peptide (ng/mL *min)	147	39	295	139
	AUC glucose (mg/dL *min)	3790	39	16,037	3,579

For specific aim 1, the primary outcome, AIRmax, and other measurements at day 90 will be compared between treatment groups with a linear model to adjust for transplanted islet mass and the randomization stratum, BMI (< or \geq 27 kg/m²). For aim 2, the same analysis will be performed for measurements made at 1 year and 2 years post-transplant. In addition, we will assess whether day 90 AIRmax and AIRglu measurements predict insulin independence at 1 and 2 years post-transplant using a logistic regression model. For aim 3, repeated measurements during the weeks immediately post-transplant will be summarized by peak and area under the curve for comparison by the same linear model used for aim 1, i.e., adjusting for transplanted islet mass and the randomization stratum. We will also compare the groups based on the longitudinal series of measurements using a mixed-effects linear model with fixed effects of treatment group, transplanted islet mass and randomization stratum, and a random intercept for each participant to model the correlation between repeated measurements from the same person.

POTENTIAL RISKS AND BENEFITS

Forseeable Risks

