- Insulin levels (GPAIS and IVGTT): To obtain accurate results in this population, we require an insulin assay that is resistant to interference from hemolysis. Fairview does not offer an adequate assay for this purpose. We will ship serum for insulin levels to the Northwest Lipid Research Laboratories at the University of Washington. Timed test glucose and C-peptide measures will also be run at NWLRL due to their ability to handle such timed, repeated measures specimens.
- Unmethylated insulin DNA: This specialized assay will be run by [name] lab at Yale University
- Trypsinogen, TAP, and liver injury markers: ELISA kits for the respective assays will be purchased and the laboratory assessments run by the technician in [name] lab.

For labs that require shipping, all specimens are labeled with the study ID number and contain no identifying information. Specimens are shipped overnight by FedEx on dry ice. All study personnel performing specimen shipping are trained in shipping through a session offered to research staff at the University of Minnesota. Appropriate precautions and labeling for biohazard materials are undertaken.

Visit Day	Screening	Day -1 or 0	Transplant visit*	Day 3	Day 7	Day 10	Day 14	Day 21**	Day 28**	Day 60	Day 90	Day 365	Day 730
Visit window	N/A	N/A	N/A	N/A	N/A	N/A	N/A	± 1	± 1	± 7	± 15	± 28	± 56
Req'd for Tx arms:	ALL	Etan/ A1AT	ALL	ALL	ALL	Etan	ALL	ALL	ALL	ALL	ALL	ALL	ALL
General Assessments													
Informed Consent	X												
History	X				X		X		X	X	X	X	X
Physical Exam	X				X		X		X	X	X	X	X
Hypoglycemia History											X	X	X
Insulin use (patient records), u/kg/day											X	X	X
AE assessment					X		X	X	X		X	X	X
Basic Labs/Safety													
Complete metabolic panel	X				X		X	X	X		X	X	X
CBC with plt/diff	X				X		X	X	X		X	X	X
D-dimer (safety assessment)	X		X	X	X		X	X	X				
IgA level	X												
Hepatitis B sAg and Ab	X												
Hepatitis C Ab	X												
HIV ELISA	X												
Urine pregnancy test (Fm)	X												
Manitoux skin test or Quantiferon (TB)	X												
Hemoglobin A1c	X										Quarterly through study		
EKG	X									X	X		
Metabolic Assessments													
Mixed meal test	X										X	X	X
GPAIS	X										X	X	X
IV glucose tolerance test	X										X	X	X
Continuous glucose monitor (iPro)											X	X	X
C-peptide: glucose (fasting)											X		
C-peptide and glucose (random)						X		X		X			
Mechanistic Assessments													
Inflammatory Cytokines*			X	X	X								

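### The model for AIRmax and the other metabolic measures leaves out the screening value of the same measure, although it is already scheduled in every arm

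*Combined protocol and SAP*

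**What the plan says.** The section SAMPLE SIZE AND PLAN FOR DATA ANALYSIS states that AIRmax and the other day 90 measures "will be compared between treatment groups with a linear model to adjust for transplanted islet mass and the randomization stratum, BMI". It carries the model forward: "For aim 2, the same analysis will be performed for measurements made at 1 year and 2 years post-transplant". For aim 3 it restates the covariates as "the same linear model used for aim 1, i.e., adjusting for transplanted islet mass and the randomization stratum", which confirms that the list has two entries. Nothing in the text available adds a screening value or analyses change from screening. A short stretch after the termination criteria was not in the copy reviewed.

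The screening values are due to exist. The synopsis (Study Procedures) includes screening/baseline among its visits and says "The following metabolic testing will be performed at each visit", naming all three tests. The list under Subject screening visit includes "Glucose potentiated arginine-induced insulin secretion" and "IV glucose tolerance test" as well as the mixed meal test. The detailed visit schedule marks all three at screening and requires that visit of all arms.

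**The concern.** The plan schedules a pre-treatment measurement of its own primary endpoint and gives it no part in the comparison, without stating a reason. With 15 patients per arm and a trial meant to pick one agent for further development, a prognostic covariate already being collected is one of the few ways to gain precision without more patients.

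Randomisation is stratified on BMI only, so baseline beta-cell function is balanced by chance alone. Two arms of 15 differ by more than 0.5 SD on any given baseline measure about 17% of the time (normal approximation: P(|Z| > 0.5/√(2/15)) = P(|Z| > 1.37)). This does not bias the comparison. If the screening value is prognostic, however, part of the residual variance could be removed and is not.

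**Working it through.** **Inputs from the protocol.** 15 per arm; 80% power for 1.06 within-group SD; AIRmax mean 137 and SD 31 mU/mL from n = 10; stated detectable difference 33 mU/mL. Alpha and sidedness are not stated. Two-sided 0.05 without multiplicity adjustment is inferred because it reproduces the stated figure.

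**The plan's own figure.** Two-sample t-test, df = 28, noncentrality 1.06 × √(15/2) = 2.903, critical t = 2.048. Power is 80.0%. Then 1.06 × 31 = 32.9 mU/mL (stated 33), and 33/137 = 24%. The stated figures reproduce and take no credit for any covariate.

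**Method for the comparison.** Let r be the partial correlation of screening with day 90 AIRmax, given islet mass and BMI stratum. The difference is set at 1.06 times the residual SD of the planned model. Every covariate is charged for the variance of estimating it:

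- Planned model (2 covariates): variance factor 41/39, df = 45 − 3 − 2 = 40.
- With screening value (3 covariates): variance factor (41/38)(1 − r²), df = 39.
- Noncentrality = 1.06 × √(7.5 / factor).

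Planned: 2.903/√1.0513 = 2.831, critical t 2.021, power 78.9%. 
Screening added: r = 0 gives 2.795 and 77.8%; r = 0.3 gives 2.930 and 81.5%; r = 0.5 gives 3.227 and 88.2%. The two models have equal power at r = 0.164.

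**Simulation.** 100,000 trials per r, three arms of 15, covariates independent and all estimated, pairwise contrast, Monte Carlo SE about 0.13 points:

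| r | Planned, % | Screening added, % | Noncentral t, screening added, % |
|---|---|---|---|
| 0 | 78.8 | 77.7 | 77.8 |
| 0.1 | 78.9 | 78.2 | 78.2 |
| 0.16 | 79.1 | 79.0 | 78.8 |
| 0.2 | 78.9 | 79.5 | 79.4 |
| 0.3 | 79.1 | 81.7 | 81.5 |
| 0.5 | 78.9 | 88.2 | 88.2 |

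If BMI stratum is taken as balanced across arms, each figure rises by about one point and the differences stay the same.

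**Detectable difference at 80% power**, taking SD 31 as the residual SD (an assumption; the protocol's SD is unadjusted):

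- Planned: 1.075 × 31 = 33.3 mU/mL.
- Screening added: 1.090 × 31 = 33.8 (r = 0); 1.039 × 31 = 32.2 (r = 0.3); 0.944 × 31 = 29.3 (r = 0.5).
- If islet mass and BMI stratum explain 25% of the variance (assumed), all are multiplied by √0.75: 28.9 planned; 29.3, 27.9 and 25.3.

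**Missing screening values.** The protocol gives no rate. Assuming 3 of 45 are missing, simulated power at r = 0, 0.3 and 0.5 is 77.7%, 81.4% and 87.5% with mean replacement, against 74.4%, 78.5% and 85.5% when those patients are dropped.

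**The case against.** The strongest objection is that the benefit depends wholly on r, which the documents do not give, and that their content points to a low value.

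- Screening tests the native pancreas, which is then removed; day 90 tests the engrafted islets. The usual argument for adjusting on the same measure is weaker when the organ differs.
- The Background says "However significant variability in diabetes outcomes is seen for any given transplanted islet mass" and attributes most of it to the gap between transplanted and engrafted mass, which a test before surgery cannot see.
- Transplanted islet mass is already in the model and may carry much of the same information.
- Exclusion criterion 1 ("fasting blood glucose >115 mg/dl, or hemoglobin A1c level >6.0"%) narrows the screening range.

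Below r of about 0.16 the change loses a little power. The SD of 31 also comes from 10 patients tested more than a year after transplant; its 95% interval, assuming normality, is about 21 to 57. The mU/mL differences above are therefore illustrations. The calculation covers AIRmax with a single r and does not establish a gain for the other measures or for years 1 and 2. Finally, changing the primary model of an open-label trial is defensible only before outcomes are compared by arm.

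All of this stands, and it limits the claim to a possible gain. It does not remove the asymmetry: about one point of power at risk, against two to three points gained at r = 0.3 and about nine at r = 0.5.

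**Conclusion.** The point holds as an optional, inexpensive improvement. The planned model is valid, the omission introduces no bias, and the stated 1.06 SD and 33 mU/mL are correct for an unadjusted t-test. At a difference of 1.06 residual SD, adding screening AIRmax moves power from about 79% to 78% if it has no prognostic value, to about 82% at r = 0.3 and to 88% at r = 0.5. These figures assume 15 evaluable patients per arm, two-sided 0.05 without multiplicity adjustment, a linear relation, and covariates independent of one another. That the screening value is omitted is certain from the text. Whether including it would help is not known, since r is not reported.

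**What to change.** 1. Keep transplanted islet mass and BMI stratum. Before any day 90 comparison by arm, pre-specify screening AIRmax as an additional covariate in the primary model. Do the same for ACRmax, AIRglu, ACRglu, AUC C-peptide and AUC glucose, each with its own screening value, at day 90, year 1 and year 2.
2. State that a missing screening value is replaced by the mean of that covariate over all arms, so that no patient is dropped.
3. Leave the insulin dose and HbA1c analyses as planned. Insulin dose has no screening value in the schedule. HbA1c has one, but it does not come from the three stimulation tests and was not part of this calculation.

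The cost is analysis-plan wording, with no new visit, sample or patient. The statistical cost is one residual degree of freedom and the variance of estimating one more coefficient, about one point of power if the screening value is not prognostic. If arm-level day 90 results have already been seen, the adjusted model should be reported as a sensitivity analysis only.

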Seventy-five percent of the TPIAT patients seen at the University of Minnesota are referred from out of state, and must travel by airplane or prolonged car trip, and stay overnight at a hotel, to participate in the study. Thus, it is not possible to reliably get patients back for study visits without providing some compensation for travel expenses. The study will reimburse patients who are from more than 60 miles away from the study center for mileage and/or airfare, airport transportation, meals (\$25/day), and hotel up to a total maximum reimbursement for travel of \$750 per visit at the day 90, 365, and 730 follow up visits (when the extended metabolic testing is performed). Screening can be coordinated during the patient's preoperative visit in the week prior to surgery; however, because this will often require one additional night in Minnesota, we will provide reimbursement for one night's hotel, up to \$250. In addition, because the metabolic tests are cumbersome, time consuming, and require a morning off of work, both local patients and those who travel will be given a stipend of \$50 per study day (\$100 total for 2 days) for completing the metabolic testing at each follow up interval. This is consistent with standard stipends provided to participants in diabetes studies at our institution.

Recruitment and advertisement materials

The study will include a one page informational handout which briefly describes the purpose of the study and the medications being tested. This hand out will include an "opt out" phone number that the patients can call if they do not wish to be contacted with any additional information. In addition, as per standard guidelines for clinical trials, the study will be posted on clinicaltrials.gov. It will be clearly emphasized that participation in a study is not required to have TPIAT surgery.

Description of the informed consent process

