Design and Methods to Evaluate Specific Aim #2

SPECIFIC AIM #2: To gather pilot data on the long-term impact of etanercept or alpha-1 antitrypsin administered during the peri-transplant period by evaluating islet function at 1 and 2 years post-transplant, as assessed by area under the curve for C-peptide on mixed meal tolerance testing (oral stimuli), acute insulin response to glucose-potentiated arginine stimulation (IV stimuli), and insulin requirements (units/kg/day) at 1 and 2 years post-TPIAT.

Hypothesis 1: AIRmax, AIRglu, and AUC C-pep from metabolic testing performed at yearly intervals post-transplant will be greater in the A1AT-treated patients and etanercept-treated patients, compared to controls.

Hypothesis 2: Mean daily insulin requirements (units/kg/day) will be lower in the A1AT-treated group vs control and in the etanercept treated vs control.

Hypothesis 3: AIRmax and AIRglu at 3 months will predict insulin independence at 1 year and 2 years post-transplant.

For specific aim #2, patients will return to the study center at day 365 ± 28 days and 730 ± 56 days post-transplant for repeat metabolic testing. Testing performed will be identical to that described under approach for specific aim 1. Both insulin use and the proportion of patients insulin independent will be recorded.

As an exploratory analysis, patients will continue to be followed yearly by a telephone or face-to-face visit, depending on whether they are returning to UMN for clinical care, at which time mean daily insulin use will be recorded, and records will be reviewed for home blood glucometer results, hemoglobin A1c level, and mixed meal fasting and stimulated glucose and C-peptide performed at the patient's local lab, per our usual routine for clinical follow up.

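### Aim 2 analyses years 1 and 2 one visit at a time, so a patient without that visit's test drops out of the comparison although the same test was done at day 90; a joint model is a cheap, modest improvement

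*Combined protocol and SAP*

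**What the plan says.** All analysis text is in the section on sample size and plan for data analysis.

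- **Aim 1.** The primary outcome and "other measurements at day 90 will be compared between treatment groups with a linear model to adjust for transplanted islet mass" and for the BMI randomization stratum.
- **Aim 2.** "For aim 2, the same analysis will be performed for measurements made at 1 year and 2 years post-transplant". No earlier visit enters as a covariate or as a joint outcome. Day-90 AIRmax and AIRglu are linked to later results only as predictors of insulin independence in a logistic model.
- **Aim 3.** "For aim 3, repeated measurements during the weeks immediately post-transplant will be summarized by peak and area under the curve", and then: "We will also compare the groups based on the longitudinal series of measurements using a mixed-effects linear model". The fixed effects listed are treatment group, islet mass and stratum, with a random intercept.

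On data collection, the methods for Aim 2 state that "patients will return to the study center at day 365 ± 28 days and 730 ± 56 days post-transplant for repeat metabolic testing". They add: "Testing performed will be identical to that described under approach for specific aim 1".

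On attendance, the travel reimbursement and compensation plan says: "Seventy-five percent of the TPIAT patients seen at the University of Minnesota are referred from out of state". It also says that "it is not possible to reliably get patients back for study visits without providing some compensation for travel expenses". It then provides reimbursement of up to $750 for each of the day-90, day-365 and day-730 visits, plus a $100 stipend for the two test days.

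**The concern.** A model fitted to one visit uses only patients with a result at that visit. A patient tested at day 90 who misses the year-1 trip is therefore left out of the year-1 contrast, and the day-90 result from the same test is not used.

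Two things are at stake. The first is precision in a trial of 15 per arm. The second is bias. Suppose patients with poorer early graft function return less often and a drug improves that function. More poor grafts are then lost from control than from the drug arm, and the contrast among those tested shrinks toward no effect.

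The endpoints concerned are AIRmax, ACRmax, AIRglu, ACRglu and the mixed-meal AUCs at years 1 and 2, which the protocol lists among its key secondary endpoints.

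**Working it through.** **1. The plan's own figure.** A two-sample t-test with 15 per arm, 28 degrees of freedom and 80% power gives a detectable difference of 1.060 SD. Two-sided alpha 0.05 is assumed because the plan states none. For AIRmax, 1.06 × 31 = 32.9 mU/mL (plan: 33), and 33/137 = 24%. The figure reproduces, and it presumes 15 results per arm.

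**2. Fewer results per arm.** The same formula with m missing per arm:

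| Missing | Results per arm | Power at 1.06 SD | Detectable AIRmax difference (mU/mL) |
|---|---|---|---|
| 0% | 15 | 80% | 32.9 |
| 10% | 13.5 | 75% | 34.8 |
| 20% | 12 | 70% | 37.1 |
| 30% | 10.5 | 64% | 40.0 |

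This is mostly the cost of losing data. A joint model recovers only part of it (step 4).

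**3. Could the mixed model already cover Aim 2?** Its sentence follows the Aim 3 sentence on the early post-transplant weeks. Its listed fixed effects contain no visit or treatment-by-visit term, so as written it would not yield a year-1 or year-2 contrast.

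**4. Precision when missingness is random.** Let ρ be the within-arm correlation between day 90 and year 1, and R² the share of variance explained by islet mass at each visit. If islet mass acts alike at both visits, the correlation left after adjustment is r = (ρ − R²)/(1 − R²). In large samples the variance ratio (visit-by-visit over joint) is 1/(1 − m r²). With m = 0.20:

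| ρ | R² | r | Ratio |
|---|---|---|---|
| 0.8 | 0.3 | 0.5/0.7 = 0.714 | 1/(1 − 0.2 × 0.510) = 1.11 |
| 0.8 | 0.5 | 0.3/0.5 = 0.60 | 1/(1 − 0.2 × 0.36) = 1.08 |
| 0.6 | 0.3 | 0.3/0.7 = 0.429 | 1/(1 − 0.2 × 0.184) = 1.04 |
| 0.6 | 0.5 | 0.1/0.5 = 0.20 | 1/(1 − 0.2 × 0.04) = 1.01 |

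Simulation at 15 per arm gives about 7–14% extra variance at ρ = 0.8 and about 0–4% at ρ = 0.6. There is no bias in this case.

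**5. Bias when return depends on day-90 function.** The simulation used 8,000 two-arm trials per setting with 15 per arm, complete day-90 data and a true effect of 1.06 SD at both visits. Logit(missing) was −1.1 or −0.6, minus 1.0 × the day-90 value in SD units from the control mean. This gives 29%/14% or 38%/20% missing (control/drug). The visit-by-visit model was adjusted for islet mass. The joint estimate regressed year 1 on day 90, arm and islet mass among those tested, then added the day-90 slope times the adjusted day-90 arm difference in all patients. BMI stratum was not simulated.

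| ρ | R² | Visit-by-visit, 29%/14% | Visit-by-visit, 38%/20% | Joint |
|---|---|---|---|---|
| 0.8 | 0.3 | 1.00 | 0.99 | 1.06–1.07 |
| 0.8 | 0.5 | 1.03 | 1.01 | 1.06 |
| 0.6 | 0.3 | 1.02 | 1.02 | 1.06 |
| 0.6 | 0.5 | 1.05 | 1.04 | 1.06 |

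Across repeated runs the shortfall is about 3–8% at ρ = 0.8 and 1–4% at ρ = 0.6. On the AIRmax scale, 0.03 × 1.06 × 31 = 1.0 to 0.08 × 1.06 × 31 = 2.6 mU/mL at ρ = 0.8. At ρ = 0.6 it is 0.3 to 1.3 mU/mL.

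Missingness, correlations, R², and the size and persistence of the effect are all assumptions; the documents give none for these visits.

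**The case against.** **The protocol does not say that patients fail to return.** A reader might infer this from the travel section. The sentence is conditional on there being no compensation, and the trial provides compensation. No year-1 or year-2 loss is projected; the only allowance is 48 randomized for 45 at day 90. This stands. Missed trips are a foreseeable risk that the trial mitigates, not a predicted failure.

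**The planned islet-mass adjustment already removes part of any selection.** This stands. Without that covariate the first setting gives about 0.97 SD, a shortfall of roughly 9%, and it is tempting to quote that figure. It does not describe the planned analysis, because the background section presents islet mass as an important predictor of outcome.

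**The assumptions favour finding a bias.** Largely true. Halving the dependence of return on day-90 function gives about 1.03 SD (3% low) even without islet mass. If the drug has no effect and return works alike in both arms, no bias arises.

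**The effect is small against the noise.** True. In the first setting, with islet mass in both models, root mean squared error at ρ = 0.8 is 0.30–0.35 SD visit by visit and 0.29–0.34 SD jointly. At ρ = 0.6 the two are essentially equal.

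**Excluding patients is nowhere written.** Correct. It follows from a single-visit model with no missing-data method in the available text. The intent-to-treat statement concerns follow-up after stopping drug and does not supply a method.

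None of this gives a reason to leave the day-90 result out of the later contrasts.

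**Conclusion.** The point holds as a cheap improvement of modest size. As written, Aim 2 does not use a patient's day-90 result when the year-1 or year-2 test is missing.

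Under the stated assumptions the visit-by-visit estimate is about 3–8% too small at correlation 0.8 and 1–4% at 0.6, while the joint estimate is essentially unbiased. With 20% missing at random the only cost is variance: about 7–14% at correlation 0.8 and 0–4% at 0.6. If few visits are missed or the correlation is low, the gain is close to nothing.

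A reader might infer that the trial's main conclusion or its choice of agent is at risk. The documents do not support that. Selection rests on day-90 function and early mechanistic data, and Aim 2 is described as pilot data. The binary endpoints are also outside the point. So is insulin dose, because patients keep logs and send them at least monthly, so a missed trip need not lose it. Patients never tested at day 90 gain little or nothing from the change.

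**What to change.** For AIRmax, ACRmax, AIRglu, ACRglu and the mixed-meal AUCs, replace the Aim 2 sentence with one likelihood-based repeated-measures model of days 90, 365 and 730. Specify:

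- treatment, visit and treatment-by-visit effects;
- visit-specific effects of islet mass and BMI stratum;
- an unstructured 3 × 3 covariance matrix;
- small-sample degrees of freedom, for example Kenward–Roger.

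Take the year-1 and year-2 contrasts from this model and keep the visit-by-visit model as a sensitivity analysis. Leave the day-90 primary analysis as it is. Report the number tested at each visit by arm, with the day-90 results of those later tested and not tested.

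The cost is a paragraph of wording and a few lines of code, with no new data. The drawback is reliance on data being missing at random given the observed results. That is weaker than what the visit-by-visit model needs, but it still fails if return depends on later graft function that day 90 does not capture.
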